## 1. SYNOPSIS

Trial Title	WAVECREST 2 Trial: W AveCrest V s. Watchman Transsc E ptal LAA Closure to R Educe AF-Mediated S Troke 2
Name of Investigational Device	Coherex WaveCrest ® Left Atrial Appendage Occlusion System
Purpose	To evaluate the safety and effectiveness of the Coherex WaveCrest Left Atrial Appendage Occlusion System
Intended Use	The Coherex WaveCrest Left Atrial Appendage Occlusion System is a percutaneous transcatheter device intended to be used for closure of the left atrial appendage (LAA)
Design	Prospective, multicenter, randomized, active control, clinical trial of the Coherex WaveCrest Left Atrial Appendage (LAA) device compared to the Watchman ® LAA device for the reduction in risk of ischemic stroke or systemic embolism in subjects with non-valvular atrial fibrillation who have an appropriate rationale to seek a non-pharmacologic alternative to chronic oral anticoagulation (OAC).
Blinding	
The following personnel will be blinded to the randomization assignment and treatment received:
 
 
• Neurology personnel evaluating subject, to the extent possible
 
• Clinical Events Committee (CEC) that will adjudicate primary safety and effectiveness events, death (cardiovascular vs. non-cardiovascular), and bleeding category
 
• Investigator’s staff administering the Questionnaire for Verifying Stroke-Free Status (QVSFS), the modified Rankin Scale (mRS), and the National Institutes of Health Stroke Scale (NIHSS) questionnaires
 

Devices Used	Watchman LAA Closure Device and Delivery Sheath WaveCrest Left Atrial Appendage Occlusion System and Delivery Sheath
Subject Population	The subject population will include participants $\geq 18$ years old diagnosed with non-valvular atrial fibrillation and a CHADS 2 score $\geq 2$ or a CHA 2 DS 2 -VASc score $\geq 3$ who have an appropriate rationale to seek a non-pharmacologic alternative to chronic oral anticoagulation.
Definitions	See protocol definitions in Appendix I: Acronyms and Definitions
Primary Effectiveness Endpoint	Composite rate of ischemic stroke or systemic embolism at 24 months
Primary Safety Endpoint	
Composite rate of:
 
 
• All cause death; or
 
• Procedure- or device-related complications requiring percutaneous or surgical intervention through 45 days post-procedure; or
 
• Major bleeding
 

	Title: The WAVECREST 2 Trial  Clinical Investigational Plan	Doc. #: CHX_IP014	Rev: H
---	--	-----------------------------	------------------

Secondary Endpoints	
 
• Rate of ischemic stroke or systemic embolism with the WaveCrest device in comparison to the CHADS2 and CHA2DS2-VASc imputed risk of ischemic stroke or systemic embolism in the absence of anticoagulant therapy
 
• Rate of LAA closure (gap ≤ 5mm) at 45 days
 

Descriptive Safety Endpoints	
 
• Components of the composite primary safety endpoint through 45 days post-procedure
 
• The rates of stroke (all types) or pericardial effusion through 45 days post-procedure
 
• Pericardial effusion requiring surgical drainage through 7 days post-procedure or at hospital discharge, whichever is later
 
• Device- or procedure-related Serious Adverse Events (SAEs) reported by site at 45 days, 6 months, and at each annual follow-up period
 
• All-cause mortality 45 days, 6 months, and at each annual follow-up period
 
• Cardiovascular mortality at 45 days, 6 months, and at each annual follow-up period
 

Descriptive Effectiveness Endpoints	
 
• Primary effectiveness endpoint event rate at 6 months, 1 year, 3 years, 4 years and 5 years
 
• Composite of all stroke, systemic thromboembolism, or TIA at 45 days, 6 months and at each annual follow-up period
 
• Landmark analysis of primary effectiveness endpoint from the 45-day visit to the time of each annual follow-up period
 
• Landmark analysis of the incidence of ischemic stroke from 6 months following device implantation and discontinuation of oral anticoagulant and dual antiplatelet therapy
 
• Composite of all-cause stroke at 45 days, 6 months, and at each annual follow-up period
 
• Incidence of thrombus on the surface of the device at 45 days, 1 year, and throughout all follow-up
 
• Strokes adjudicated as ischemic, hemorrhagic, or indeterminate at 45 days, 6 months, and at each annual follow-up period
 
• Strokes adjudicated as major or minor at 45 days, 6 months, and at each annual follow-up period
 
• Stroke adjudicated as cardioembolic in origin at 45 days, 6 months, and at each annual follow-up period
 
• Freedom from oral anticoagulants after each protocol-required follow-up visit
 
• Number of devices used per subject
 
• Procedural success
 

	Title: The WAVECREST 2 Trial  Clinical Investigational Plan	Doc. #: CHX_IP014	Rev: H
---	--	-----------------------------	------------------

	
 
• Technical success
 
• Device success
 
• LAA Closure as determined by Echocardiography Core Lab (ECL) at 45 days, 6 months, and at 1 year
 
• Procedure time, device duration, contrast volume used, and fluoroscopy time
 

Inclusion Criteria	
 
1. Documented evidence of paroxysmal, persistent, or permanent non-valvular atrial fibrillation
 
2. At least 18 years of age
 
3. Calculated CHADS2 score <math>\geq</math> 2 or CHA2DS2-VASc score <math>\geq</math> 3
 
4. Indication for warfarin therapy with an appropriate rationale to seek a non-pharmacologic alternative to chronic oral anticoagulation
 
5. Willing and able to comply with post-implant anticoagulation and antiplatelet regimen
 
6. Willing to participate in the required follow-up visits and tests
 
7. Subject has been informed of the nature of the trial, agrees to its provisions and has provided written informed consent as approved by the Institutional Review Board/Ethics Committee (IRB/EC) at the site
 

Exclusion Criteria	
 
1. Atrial fibrillation (AF) due to a reversible cause (e.g. thyrotoxicosis or post-operative)
 
2. Known contraindication and/or allergy to warfarin, nickel, aspirin, intravenous contrast, or P2Y12 inhibitors (clopidogrel, ticagrelor, and prasugrel), which cannot be adequately pre-medicated or desensitized
 
3. Conditions other than atrial fibrillation requiring long-term anticoagulation therapy
 
4. Contraindications to percutaneous catheterization procedures
 
5. Prior surgical LAA occlusion/exclusion or implanted with LAA occlusion device, or any prior attempt of such procedures
 
6. Prior percutaneous or surgical closure of a patent foramen ovale or atrial septal defect
 
7. Inability or unwillingness to take oral anticoagulation for 45 days post-procedure
 
8. New York Heart Association Class IV heart failure
 
9. Prior cardiac transplant, history of mitral valve replacement, or transcatheter mitral valve intervention, or any mechanical valve implant
 

 	Title: The WAVECREST 2 Trial  Clinical Investigational Plan	Doc. #: CHX_IP014	Rev: H
--	--	-----------------------------	------------------

	
 
10. History of symptomatic carotid, intervertebral, or intracranial artery occlusion or stenosis without revascularization with the exception of known occlusion without symptoms > 6 months
 
11. Modified Rankin Scale Score <math>\geq</math> 4
 
12. Chronic resting heart rate > 110 bpm
 
13. Congenital or other clinically significant cardiac anomalies requiring cardiac surgery or interventional repair
 
14. Stroke or transient ischemic attack (confirmed by Neurologist) within 60 days prior to enrollment
 
15. Myocardial infarction within 60 days prior to enrollment
 
16. Sepsis or any active infection requiring oral antibiotic therapy within 14 days or intravenous antibiotic therapy within 30 days prior to enrollment
 
17. Surgical or interventional cardiovascular and non-cardiovascular procedure including cardioversion within 30 days prior to enrollment or AF ablation within 60 days prior to enrollment or any planned general surgery or planned interventional procedure within 90 days after enrollment or any planned cardiac surgery
 
18. On renal replacement therapy, serum creatinine > 3.0 mg/dl (265 <math>\mu</math>mol/L) or calculated creatinine clearance < 25 ml/minute
 
19. Thrombocytopenia (<60,000 platelets/mm^3), leucopenia (white blood cell count < 3,000 cells/mm^3), or anemia (hemoglobin concentration < 10 gram/deciliter)
 
20. Any medical disorder or psychiatric illness that would interfere with successful completion of the trial
 
21. Currently participating in an investigational drug trial or another device trial that has not completed the primary endpoint (trials requiring extended follow-up for products that are commercially available are not considered investigational trials). Concurrent enrollment in the ACC LAAO Registry is permitted.
 
22. Subject belongs to a vulnerable population (see definition in Appendix I: Acronyms and Definitions)
 
23. Any condition that would reduce life expectancy to less than 2 years
 
24. Women of childbearing potential who are, or plan to become pregnant during the time of the trial (method of assessment per physician discretion)
 

Echocardiographic Exclusion Criteria	
 
1. Estimated left ventricular ejection fraction < 30%
 
2. Mitral valve stenosis defined as valve area < 1.5cm^2, mean gradient > 6mmHg, or any mitral valve deformity consistent with rheumatic valvular disease
 

	Title: The WAVECREST 2 Trial  Clinical Investigational Plan	Doc. #: CHX_IP014	Rev: H
---	--	-----------------------------	------------------

	
 
3. Aortic valve stenosis defined as valve area <math>\leq 1.0\text{cm}^2</math> or mean gradient <math>>30\text{mmHg}</math>
 
4. Circumferential pericardial effusion <math>> 10\text{mm}</math>, loculated pericardial effusion with the largest dimension <math>> 10\text{ mm}</math>, or symptomatic pericardial effusion of any size
 
5. Evidence of intracardiac thrombus (including in left atrial appendage, left ventricle or elsewhere)
 
6. Cardiac tumor or myxoma
 
7. Atrial septal defect that warrants closure
 
8. Complex atheroma in the ascending aorta or aortic arch as evidenced by mobile plaque.
 
9. Left Atrial Appendage size and shape are unsuitable for closure with a WaveCrest or Watchman device
 

Pre-Procedure Care	
The following Baseline steps are recommended to be performed within 30 days prior to randomization but must be completed within 90 days prior to randomization (or within 90 days prior to treatment of roll-in subject):
 
 
• Document medical history (if not previously documented).
 
• Document appropriate rationale to seek a non-pharmacologic alternative therapy
 
• Perform physical exam
 
• Administer Quality of Life (QoL) SF-36 questionnaire
 
• Blood work to document CBC (HGB, WBC, platelets), and serum creatinine with INR and pregnancy as necessary
 
• CHADS2 and CHA2DS2-VASc score (see Appendix II for calculation of CHADS2 and CHA2DS2-VASc scores).
 
• Calculate HAS-BLED score (see Appendix II for calculation of HAS-BLED score)
 
• A trial staff member must administer the QVSFS to the subject (see Appendix III).
 
• All subjects must undergo NIHSS and mRS. Both must be administered by board-certified study Neurologist or trained and certified trial personnel (Appendix IV: Neurologic Assessments)
 
• If the subject has a history of stroke or TIA or if the baseline QVSFS score is <math>> 0</math> the subject must be seen by a board-certified study Neurologist, including review of the following: 
 
○ Brain imaging (MRI unless contraindicated, then CT)
 
○ If an imaging study is available following the prior stroke or TIA, a new study is not required per study Neurologist’s discretion
 
○ Completed NIHSS & mRS
 
 
 

	Title: The WAVECREST 2 Trial  Clinical Investigational Plan	Doc. #: CHX_IP014	Rev: H
---	--	-----------------------------	------------------

	
 
• Perform baseline TEE. If thrombus is detected, the subject may undergo a 6-week course of anticoagulation followed by a repeat TEE. The subject may be re-evaluated after appropriate anticoagulation therapy and considered for device placement following documentation of absence of thrombus. The timeline from initial screening subject to the end of thrombus treatment must be treated within 90 days prior to randomization - or treatment, for roll-in subjects.
 

Post-Procedure Care	
Immediately post-procedure for 45 days post-implant:
 
 
• All subjects must have a TTE to rule out pericardial effusion prior to discharge.
 
• Subjects receiving a Watchman device should begin/continue/resume warfarin therapy and aspirin per the product Directions for Use (DFU). [Note: Alternative vitamin K antagonists (e.g., acenocoumarol or phenprocoumon) may be used according to geographic standard of care.]
 
• Subjects receiving a WaveCrest device are required to start clopidogrel 75 mg daily and 75-100 mg aspirin daily starting 12-48 hours after the procedure (prasugrel or ticagrelor are allowable for clopidogrel intolerance, however, prasugrel is contraindicated in subjects with a history of prior stroke/TIA and both prasugrel and ticagrelor are contraindicated in subjects with a history of hemorrhagic stroke).
 
 
45 days post-implant
 
 
• At 45 days (+15/- 5 days) post-implant, a device assessment with TEE is to be performed.
 
• Warfarin cessation in the Watchman arm is per Watchman DFU but is recommended if peri-device flow by TEE is <math>\leq 5</math>mm. If an adequate seal is not demonstrated, Watchman DFU recommendation for anticoagulation should be followed until peri-device flow <math>\leq 5</math>mm is observed.
 
• When Watchman arm subjects stop warfarin, clopidogrel should be started per the product DFU.
 
• Evidence of device thrombus in either arm is recommended to be treated with a 6-week course of warfarin (+/- aspirin) and a repeat TEE. For subjects in the WaveCrest arm, clopidogrel should be stopped prior to initiating anticoagulation therapy.
 
• Subjects treated with the WaveCrest device with no evidence of device thrombus will continue dual antiplatelet therapy (DAPT) regardless of peri-device flow until 3 months post-implantation.
 
 
3 months post-implant

	Title: The WAVECREST 2 Trial  Clinical Investigational Plan	Doc. #: CHX_IP014	Rev: H
---	--	-----------------------------	------------------

	
 
WaveCrest arm subjects discontinuing clopidogrel (or P2Y12 inhibitor) must remain on 75-100mg aspirin daily indefinitely.
 
 
6 months post-implant
 
 
Subjects with peri-device flow >5mm at 45 days will undergo a TEE at 6 months.
 
Watchman arm subjects discontinuing warfarin and clopidogrel (or P2Y12 inhibitor) should take daily aspirin per the Watchman DFU indefinitely.
 
																																																																		
Number of Trial Sites	Up to 100 sites will participate in the trial in North America, Europe, Australia, and Asia																																																																		
Sample Size	
 
Up to 1,550 subjects will be randomized in a 1:1 ratio between the WaveCrest and Watchman devices. The trial design offers at least 80% power to establish non-inferiority for the effectiveness and safety hypotheses across the range of possible event rates.
 
Sites will be allowed up to 5 roll-in cases (up to 2 per operator) prior to randomization for a total of up to 500 roll-in subjects.
 
Up to 2,050 total subjects will be enrolled
 
																																																																		
Enrollment Phase	The enrollment phase is expected to last between 2 and 3 years.																																																																		
Follow-up Evaluations	
Office follow-up: at 45 days, 6 months, 1, 2, 3, 4 & 5 years  Phone follow-up: at 3 month & 1.5, 2.5, 3.5, and 4.5 years  Transesophageal echocardiograms (TEE):
 
 
45-day visit
 
6-month visit (if LAA closure is not established at 45-day visit)
 
1-year visit
 
 
Summary of Study Assessments
 
  
 Test	Screening /Baseline	Treatment	Discharge	Office F/U	Phone F/U	
   
 Med Hx	X					
 
 Phys Exam	X	X	X	X		
 
 Blood work	X					
 
 QVSFS	X			X	X	
 
 QoL	X			X		
 
 Neuro eval	X	X (with stroke symptoms or QVSFS>0)*	
 
 TEE	X	X		X*		
 
 TTE			X			
 
 AE eval	X	X*	X	X	X	
 
 Med review	X	X	X	X	X	
  
 
* - see additional details in Table 4 of the CIP below
	Test	Screening /Baseline	Treatment	Discharge	Office F/U	Phone F/U	Med Hx	X					Phys Exam	X	X	X	X		Blood work	X					QVSFS	X			X	X	QoL	X			X		Neuro eval	X	X (with stroke symptoms or QVSFS>0)*				TEE	X	X		X*		TTE			X			AE eval	X	X*	X	X	X	Med review	X	X	X	X	X
Test	Screening /Baseline	Treatment	Discharge	Office F/U	Phone F/U																																																														
Med Hx	X																																																																		
Phys Exam	X	X	X	X																																																															
Blood work	X																																																																		
QVSFS	X			X	X																																																														
QoL	X			X																																																															
Neuro eval	X	X (with stroke symptoms or QVSFS>0)*																																																																	
TEE	X	X		X*																																																															
TTE			X																																																																
AE eval	X	X*	X	X	X																																																														
Med review	X	X	X	X	X																																																														
Echocardiography Core Lab	The echocardiography core lab will review all TTEs/TEEs performed at baseline, implant procedure (all echocardiographs), discharge, 45																																																																		

[figure not shown]
	Title: The WAVECREST 2 Trial  Clinical Investigational Plan	Doc. #: CHX_IP014	Rev: H
---	--	-----------------------------	------------------

	days, 6 months (if applicable), and 1-year follow-up as well as all TTEs/TEEs conducted during neurology evaluations for closure and thrombus and any TTEs/TEEs conducted at outside facilities (e.g., for adverse events).
Neurological Evaluations	
 
• At Baseline (after enrollment, prior to randomization or procedure for roll-in subjects): 
 
○ Cerebrovascular and neurologic medical history (if not previously documented)
 
○ QVSFS
 
○ Quality of Life (QoL) questionnaire
 
○ mRS/ NIHSS
 
○ If subject has a history of a stroke/TIA or a baseline QVSFS score > 0, they must be seen by a board-certified study Neurologist to review the following: 
 
▪ Brain imaging 
 
- MRI preferred, CT if MRI contraindicated
 
- If an imaging study following the prior neurologic event is available, repeat imaging is not required per board certified Neurologist's discretion
 
 
 
▪ Completed NIHSS & mRS
 
 
 
 
 
• At study office visits and phone follow-ups, or if the subject has an unscheduled visit for stroke symptoms: 
 
○ Blinded trial personnel must administer QVSFS
 
○ Subject-reported stroke/TIA or symptoms resulting in an increase in QVSFS score > 0 since subject's most recent follow-up require a visit with board-certified study Neurologist (an Unscheduled Neurology Visit) to review/perform the following: 
 
▪ Completed mRS & NIHSS
 
▪ Brain imaging (MRI or CT if MRI is contraindicated)
 
▪ If stroke is confirmed, appropriate neurology-guided evaluation is indicated to determine stroke etiology, including the following recommended steps: 
 
- Cervical/neck artery imaging (CTA/MRA/carotid Doppler)
 
- Intracranial artery imaging (CTA/MRA/transcranial Doppler)
 
- 24-hour cardiac monitoring
 
- TEE
 
- Subject must have a mRS re-administered 90 (+/- 15) days after any confirmed stroke
 
 
 
 
 
 
 

 	Title:  The WAVECREST 2 Trial Clinical Investigational Plan	Doc. #:  CHX_IP014	Rev:  H
--	---	---------------------------------	----------------------

	Note: Personnel who administer mRS & NIHSS must be certified, properly trained and blinded to subject randomization.
--	--

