**2.2 Risk-Stratification**

Decision-making regarding the initiation of anticoagulant medication requires tools to predict both embolic and bleeding risk. Risk stratification for embolization in patients with non-valvular AF can be performed using both clinical and echocardiographic parameters. These parameters have been derived from both randomized trials and community cohorts. To identify AF patients at risk for stroke, the Atrial Fibrillation Investigators (AFI) pooled and analyzed data from five randomized stroke prevention trials in subjects with non-valvular AF. The resulting CHADS2 scoring system^41 has until recently been recommended for use to estimate embolic stroke risk in AF patients. CHADS2 is an acronym created from the first letter of five clinical parameters: **C**ongestive heart failure, **H**ypertension, **A**ge ≥ 75 years, **D**iabetes mellitus, and prior **S**troke/TIA/Thromboembolism. The CHADS2 score ranges from 0 to 6. A limitation of the CHADS2 score is that a subset of patients with a CHADS2 score of 1 may have other risk factors for embolic stroke that are not accounted for. This limitation is overcome by the use of the CHA2DS2-VASc score (which gives an additional point each for Vascular disease, Age 65 to 74 years, and female Sex). The CHA2DS2-VASc score ranges from 0 to 9. The CHA2DS2-VASc scoring system can be used to reliably identify truly low risk patients, who can be managed without antithrombotic therapy (i.e., patients with CHA2DS2-VASc score of 0). **Appendix II** explains the CHADS2 and CHA2DS2-VASc scoring systems.

Table 1 shows stroke risks for the CHA2DS2-VASc scoring system.

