**Table 1: Adjusted Stroke Rate by CHA2DS2-VASc Score**

CHA 2 DS 2 -VASc Score	Adjusted Stroke Rate (% per year)
0	0%
1	1.3%

 	Title: The WAVECREST 2 Trial  Clinical Investigational Plan	Doc. #: CHX_IP014	Rev: H
--	--	-----------------------------	------------------

CHA 2 DS 2 -VAsc Score	Adjusted Stroke Rate (% per year)
2	2.2%
3	3.2%
4	4.0%
5	6.7%
6	9.8%
7	9.6%
8	6.7%
9	15.2%

Risk of bleeding may be assessed by the HAS-BLED score. The score assigns 1 point for the presence of each of the following: hypertension, abnormal renal and/or liver function, previous stroke, bleeding tendency or predisposition, labile INRs, elderly and concomitant drugs and/or alcohol excess (**See Appendix II**). The score ranges from 0 to 9, with scores  $\geq 3$  indicating high risk of bleeding. HAS-BLED should not be used on its own to exclude patients from oral anticoagulant therapy; the score allows the clinician to identify bleeding risk factors and to correct those that are modifiable, e.g., by controlling blood pressure, removing concomitant antiplatelet or nonsteroidal anti-inflammatory drugs, and counseling the patient about reducing alcohol intake (if excessive).

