### 3.7 Steps that will be taken to control or mitigate the risks and study bias

To minimize potential clinical risks to subjects participating in this clinical trial and potential bias in the study:

- Investigators selected for this trial will not have significant equity interest in Johnson & Johnson (parent company of Coherex Medical). Physicians (or their spouses or dependent children) who receive compensation that could be affected by the outcome of this clinical trial or who have significant equity interest in Johnson & Johnson will not be selected as Investigators in this trial. Each Investigator will complete a financial disclosure form before subject enrollment, and as requested by the Sponsor during trial conduct and at the completion of the trial. A significant equity interest in Johnson & Johnson would include, for example:
  - Any ownership interest, stock options, or other financial interest whose value cannot be easily determined through reference to public prices;
  - an equity interest exceeding USD 50,000;
  - Significant payments of other sorts, which are payments that have a cumulative monetary value of more than USD 25,000, EXCLUDING the costs of conducting the trial or other clinical trials. This could include, for example, payments made to the individual or the institution to support activities (i.e., a grant to fund ongoing research, compensation in the form of equipment, or retainers for ongoing consultation or honoraria).

	Title: The WAVECREST 2 Trial  Clinical Investigational Plan	Doc. #: CHX_IP014	Rev: H
---	--	-----------------------------	------------------

- Randomization will be stratified by site and CHA2DS2-VASc score ≤ 4 vs. > 4. To ensure the randomization ratio is maintained within lower enrolling sites, randomization will be assigned in permuted blocks within site, and sites will not be aware of the randomization schedule.

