### 15.5 Secondary Effectiveness Endpoints

The first secondary effectiveness objective is to establish non-inferiority of the rate of LAA closure at 45 days for the WaveCrest arm compared to the control arm. The rate will be calculated as the number of subjects who have residual flow  $\leq 5$  mm based on the 45-day TEE divided by the number of subjects in each group with a 45-day TEE. Let  $I_{\text{WAVECREST}}$  be the 45-day LAA closure rate in the device arm, while  $I_{\text{CONTROL}}$  is the corresponding rate in the control arm. Specifically, the following null and alternative hypotheses will be tested:

$$H_0: I_{\text{WAVECREST}} - I_{\text{CONTROL}} \geq 8.0\% \text{ vs.}$$

$$H_a: I_{\text{WAVECREST}} - I_{\text{CONTROL}} < 8.0\%.$$

	Title: The WAVECREST 2 Trial  Clinical Investigational Plan	Doc. #: CHX_IP014	Rev: H
---	--	-----------------------------	------------------

The other secondary effectiveness objective is to demonstrate reduction in risk of ischemic stroke or systemic embolism with the WaveCrest device in comparison to the CHADS2 and CHA2DS2-VASc imputed risk of ischemic stroke or systemic thromboembolism in the absence of anticoagulant therapy.

The rate of ischemic stroke in subjects receiving the WaveCrest device in the Treatment Arm will be tested against a performance goal. The hypotheses to be tested are as follows:

$$H_0: I_w \geq 6.0$$

$$H_1: I_w < 6.0$$

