**APPENDIX II: CHADS2, CHA2DS2-VASc and HAS-BLED Scores**

The CHADS2 score was developed from five clinical parameters to identify non-valvular AF patients at an elevated risk for ischemic stroke. One point is added for patients who have the following: congestive heart failure, hypertension, age ≥ 75 years, and diabetes mellitus. Two points are given for patients with a prior stroke/TIA/thromboembolism. The CHADS2 score ranges from 0 to 6. A limitation of the CHADS2 score is that a subset of patients with a CHADS2 score of 1 may have other risk factors for embolic stroke. This limitation is overcome by the use of the CHA2DS2-VASc score, which is another ischemic stroke risk stratification method in subjects with non-valvular atrial fibrillation. The score assigns 1 or 2 points for each of the following risk factors: congestive heart failure, hypertension (defined as blood pressure consistently above 140/90), age ≥75 years, diabetes mellitus, prior stroke or TIA or thromboembolism, vascular disease, age 65 to 74 years, female gender. The score ranges from a minimum of 0 to a maximum of 9, with lower scores having lower risk and higher scores having higher risk for ischemic strokes. Subjects in the trial must have a minimum CHA2DS2-VASc score of 3 or a minimum CHADS2 score of 2.

CHADS 2		CHA 2 DS 2 -VASc	
Risk Factor	Points	Risk Factor	Points
Congestive Heart Failure	1	Congestive Heart Failure a	1
Hypertension	1	Hypertension	1
Age ≥ 75 years	1	Age > 75 years	2
Diabetes Mellitus	1	Diabetes Mellitus	1
Stroke/TIA/Thromboembolism	2	Stroke/TIA/Thromboembolism	2
		Vascular Disease (prior myocardial infarction, peripheral artery disease or aortic plaque)	1
		Age 65 to 74 years	1
		Female	1
Maximum Score	6	Maximum Score	9

a Heart failure with reduced ejection fraction or recent heart failure hospitalization (irrespective of ejection fraction)

	Title: The WAVECREST 2 Trial  Clinical Investigational Plan	Doc. #: CHX_IP014	Rev: H
---	--	-----------------------------	------------------

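### The Appendix II CHA2DS2-VASc table has no age row for a 75-year-old and contradicts the appendix's own prose, although the score sets entry and the randomisation stratum

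*Protocol*

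**What the plan says.** **Where the score is used.** The Protocol Synopsis and Section 4.4.1 set entry at "Calculated CHADS 2 score \geq 2 or CHA 2 DS 2 -VASc score \geq 3". Section 3.7 adds: "Randomization will be stratified by site and CHA 2 DS 2 -VASc score ≤ 4 vs. > 4". Section 4.2 repeats that stratification.

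**Where the score is defined.** Section 4.4.1, Section 6.1 and the Synopsis entry on pre-procedure care refer the site to Appendix II. It has two parts that bear on age:

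- *Prose.* The CHA2DS2-VASc factors listed include "hypertension (defined as blood pressure consistently above 140/90), age ≥75 years, diabetes mellitus", and separately "age 65 to 74 years". The prose says that factors carry 1 or 2 points but does not say which carries which. For CHADS2 it says: "One point is added for patients who have the following: congestive heart failure, hypertension, age ≥ 75 years, and diabetes mellitus".
- *Table.* The CHADS2 column has 1 point at ≥ 75. The CHA2DS2-VASc column has 2 points at > 75 and 1 point at 65 to 74.

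Protocol Section 2.2 gives the CHADS2 age item as ≥ 75 and describes CHA2DS2-VASc as the score "which gives an additional point each for Vascular disease, Age 65 to 74 years, and female Sex".

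**The concern.** The table is the only place in the visible documents that assigns points to each CHA2DS2-VASc factor, so a site coordinator or an EDC programmer would naturally work from it. Taken literally, it gives a 75-year-old fewer age points than a 74-year-old and fewer than a 76-year-old. That cannot be intended, and it contradicts the prose printed with it.

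Two operative steps depend on the result: the ≥ 3 entry route and the ≤ 4 versus > 4 stratum. If some sites follow the prose and others the table, identical patients could be admitted or stratified differently.

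**Working it through.** **Inputs.** Points per factor come from the Appendix II table. The competing age rule comes from the Appendix II prose. The entry rule is Section 4.4.1, the stratum is Sections 3.7 and 4.2, and the rates are in Protocol Table 1. Age is taken in completed years.

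**Step 1: the plan's own figures.** Summing the points over all factor combinations gives maxima of 6 (CHADS2) and 9 (CHA2DS2-VASc), as printed. The CHA2DS2-VASc maximum is 9 under either age rule, so it does not reveal the gap.

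**Step 2: age points.**

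| Age | Table (> 75) | Prose (≥ 75) |
|---|---|---|
| 74 | 1 | 1 |
| 75 | 0 | 2 |
| 76 | 2 | 2 |

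Age 75 is the only age at which the two differ.

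**Step 3: scores at age 75.** Let x = heart failure + hypertension + diabetes + 2 × prior stroke/TIA/thromboembolism, and y = vascular disease + female sex. The six yes/no factors give 2^6 = 64 profiles.

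- CHADS2 = 1 + x
- CHA2DS2-VASc by the prose = 2 + x + y
- CHA2DS2-VASc by the table = x + y

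**Step 4: entry.** If x ≥ 1, CHADS2 is at least 2 and the subject qualifies whichever age rule is used. The rule matters only when x = 0:

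- Female only: 3 by the prose, 1 by the table.
- Vascular disease only: 3 by the prose, 1 by the table.
- Both: 4 by the prose, 2 by the table.
- Neither: 2 by the prose, ineligible under both.

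So 63 profiles are eligible by the prose and 60 by the table; 63 − 60 = 3 are wrongly excluded.

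**Step 5: stratum.** The stratum changes when 2 + x + y > 4 but x + y ≤ 4, that is, when x + y is 3 or 4. Counts by x + y are the coefficients of (1 + t)^5 (1 + t²): 1, 5, 11, 15, 15, 11, 5, 1, which sum to 64. Hence 15 profiles go from 5 to 3 and 15 from 6 to 4, 30 in all. Because y is at most 2, x + y ≥ 3 forces x ≥ 1, so all 30 remain eligible through CHADS2.

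**Step 6: Table 1 rates.** A score of 5 read as 3 corresponds to 3.2 instead of 6.7% per year, and 6 read as 4 to 4.0 instead of 9.8%. Table 1 is not monotone: 8 read as 6 goes up, from 6.7 to 9.8%.

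**Step 7: how many subjects are aged 75.** The documents give no age distribution for this trial. Protocol Section 4.4.4 reports an average of about 72 years in earlier closure studies. Assuming a Normal distribution with SD 7 to 10 (my assumption), about 3.8 to 5.0% are aged 75, or about 58 to 78 of 1,550. This counts everyone aged 75, not those mis-scored. The number affected cannot be derived, because risk-factor frequencies are not given.

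**The case against.** **The prose already gives the right rule.** Sites are referred to Appendix II as a whole, and nothing visible shows that the table's version was ever applied. Randomisation runs through the EDC system, whose score logic cannot be seen. This stands: the effects above are conditional on the table being used. It does not remove the contradiction, because the prose assigns no points factor by factor.

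**It may be a reading artefact.** The point hangs on one symbol in text taken from a PDF, and a lost underline cannot be fully excluded. Against that, the CHADS2 cell in the same row came through as ≥.

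**Exact age shrinks the gap.** If > 75 is read on exact age while the lower band runs to the end of the 75th year of life, the gap is only the 75th birthday. That mixes two conventions. On exact age throughout, the lower band stops at 74.0 and the gap is the year from there to 75.0.

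**Stronger readings that the documents do not support.**

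- *That 75-year-olds score 0 in total, or are broadly excluded.* The zero is the age item only, and CHADS2 ≥ 2 admits anyone aged 75 with one further CHADS2 factor.
- *That the primary comparison is biased.* The score is fixed before randomisation and is the same whichever arm is drawn, so allocation within the assigned stratum remains valid. The possible cost is some loss of balance on actual risk.
- *That the imputed-risk objective is distorted.* Section 15.5 says the WaveCrest rate "will be tested against a performance goal", a fixed 6.0 per 100 patient-years (units in SAP Section 8.4). Mis-scoring moves neither that goal nor the observed rate, and Protocol Section 4.3.2 rules out claims on this endpoint. Only subject-level imputed risks, if computed, would change, and Table 1 shows that they need not all fall.

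**Conclusion.** The contradiction is real and lies in a scoring rule that sites must use, so it should be corrected. Its reach is limited to one year of age. If the printed table was applied, 3 of 64 profiles at age 75 (female sex and/or vascular disease as the only other points) would be wrongly excluded. The 30 profiles scoring 5 or 6 by the prose would be placed in the ≤ 4 stratum. Mis-stratification is the wider effect: it makes the stratum label, baseline score tables and any by-score summary inaccurate.

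This rests on three assumptions: the symbol was read correctly from the PDF, age is taken in completed years, and the table was followed over the prose. The counts are unweighted combinations and must not be read as patient proportions.

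**What to change.** 1. In the CHA2DS2-VASc column of the Appendix II table, change the upper age row to ≥ 75, in line with the appendix's prose and the CHADS2 column.
2. Confirm which age rule the EDC system, and any site worksheet, uses for eligibility and for the stratum.
3. If the printed table was applied, rescore subjects aged 75 for baseline tables, by-score summaries and any subject-level imputed risk. Keep the stratum as randomised wherever the stratification factor is used.

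The cost is one character, one check of the score logic and, if needed, a small rescore. No extra subjects or visits are required.
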